### **Covid-19 Sub-Study Specific Aims**

- 1) To assess patient enthusiasm for pursuing previously scheduled elective THA/TKA after the Covid pandemic. By canvassing PEPPER patients who completed enrollment and had surgery cancelled we will assess a pandemic's effects on the value patients place on elective discretionary surgery and their utilization of orthopaedic care. A supplemental survey developed in conjunction with the PEPPER Patient Advisory Board (PAB) will be sent via mail or email and completed by PEPPER enrollees whose procedure was cancelled due to Covid (estimated 300 patients; 2 months of "paused" surgical prep enrollees).
- 2) To assess the delay in rescheduling and the rate of "failure to reschedule" surgery for patients who were enrolled in PEPPER and had surgery cancelled due to Covid. Patients enrolled in PEPPER who had surgery prior to Covid-19 will provide a baseline cancellation rate compared to PEPPER patients whose surgery was cancelled from Covid. Post-Covid "failure to reschedule" rates and rescheduling delays will be computed out to 1 year to account for seasonal scheduling preferences of patients. This will inform our understanding of utilization of healthcare services for elective procedures post Covid. Patient preferences will be assessed from deployment of the PEPPER PAB endorsed survey.
- 3) To assess the relative risk of venous thromboembolism (VTE) and anticoagulant-related morbidity in Covid-exposed, recovered, and/or vaccinated patients undergoing THA/TKA. Evidence suggests an association of hypercoagulability and anti-phospholipid antibodies with Covid disease, which may increase risk of VTE after THA and TKA. We will investigate the impact of this relationship on VTE after THA/TKA.
- 4) To compare patient-reported outcomes (PRO) in cohorts having surgery before and after COVID. Validated functional outcome tools will be compared among patients before and after COVID, including the Mental Component Score from the PROMIS-10 and the GAD-2 as a marker of psychological distress. This will provide insight into how the Covid healthcare crisis may have impacted patient attitudes and its impact on PRO scores and VTE in a cohort of THA/TKA patients.

Patients involved in the Covid-19 Sub Study will complete the survey under a waiver of written consent. The survey will contain a written statement describing the reason for the survey and the research.

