Consent to participate in the study may be obtained by the study site coordinator or any other appropriately qualified study staff member. Upon obtaining informed consent, each site coordinator will collect baseline information from the patient concerning comorbidities, joint function, and general well-being data using the respective hip or knee disability and osteoarthritis outcome scores (HOOS and KOOS), the Oswestry and Charlson instruments, and the PROMIS-10 global health survey. Baseline instruments should be collected within the 3 months prior to the patient's operation.

Once consent is obtained, the surgeon will sign off on all eligibility criteria using the Surgeon Screening Confirmation Form and the patient will be considered enrolled in the PEPPER trial and eligible for randomization.

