
## 3.1.2.1. Schedule of Events

	Screening	Baseline (-3 months to -1 day)	Randomization (Surgeon Confirmation to -1 day)	Surgery (Day 0)	Post Op (Day 1)	Hospital Discharge	4 Week FU (+ 10 days)	3 Month FU (+/- 10 days)	6 Month FU (+/- 1 month)
Pre-Screen Form	X								
Screening Form	X								
Eligibility Review	X								
Electronic/ Written Informed Consent		X							
HOOS/KOOS		X					X	X	X
Oswestry Instrument		X							
Charlson Comorbidity Index		X							
PROMIS-10 Global Health Survey		X					X	X	X
Randomization			X						
Urine Pregnancy Test				X*					
Study Drug Administration (Aspirin Arm)				X (ongoing for 30 days)	X	X	X		
Study Drug Administration (Rivaroxaban Arm)				X (ongoing for 30 days)	X	X	X		
Perioperative Form						X			
AE/SAE Monitoring			X	X	X	X	X	X	X

\* Urine pregnancy test done as part of the patient's standard of care and the results will be reviewed for research purposes.

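### Covid sub-study Aim 2 takes its baseline cancellation rate only from patients who had surgery, so permanent pre-Covid cancellations are left out; Aim 4's GAD-2 comparison has no listed pre-Covid measurement

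*Protocol*

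**What the plan says.** All of this is in the Protocol.

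**Aim 2** (Covid-19 Sub-Study Specific Aims, under section 1.2) concerns rescheduling delay and failure to reschedule among enrollees whose surgery Covid cancelled. For context it adds: "Patients enrolled in PEPPER who had surgery prior to Covid-19 will provide a baseline cancellation rate", to be "compared to PEPPER patients whose surgery was cancelled from Covid". The post-Covid failure-to-reschedule "rates and rescheduling delays will be computed out to 1 year to account for seasonal scheduling preferences of patients". Aim 1 gives the size of the cancelled cohort as "estimated 300 patients; 2 months of" paused enrollees.

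**Aim 4** compares patient-reported outcomes in cohorts operated on before and after Covid, "including the Mental Component Score from the PROMIS-10 and the GAD-2 as a marker of psychological distress". The supplemental survey described in Aim 1 is to be "completed by PEPPER enrollees whose procedure was cancelled due to Covid".

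**Main-trial instruments.** Section 3.1.2 a) lists, at baseline, HOOS or KOOS, "the Oswestry and Charlson instruments, and the PROMIS-10 global health survey". Section 3.1.2 f) lists HOOS or KOOS and PROMIS-10 at follow-up. The Schedule of Events (3.1.2.1) has a row for the "PROMIS-10 Global Health Survey" at baseline, 4 weeks, 3 months and 6 months, and no row for the GAD-2.

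**The concern.** A background cancellation rate is there to show how much cancellation and non-return would have happened without the pandemic. To do that, its denominator must be everyone who was due for surgery. Aim 2 instead forms each group by how things turned out: one by having been operated on, the other by having been cancelled. The patients who carry the missing information, those who enrolled before Covid, cancelled and never came back, fall in neither group.

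What is at stake is the reading of the post-Covid failure-to-reschedule rate. Set beside a baseline in which that outcome cannot occur, ordinary drop-out from elective surgery would look like a pandemic effect.

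A smaller gap of the same kind sits in Aim 4. A before/after comparison needs a measurement made before, and the Protocol does not say where a pre-Covid GAD-2 score would come from.

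**Working it through.** The Protocol gives no sample size, power or expected rate for these comparisons, so there is no planned figure to reproduce. The check is on denominators.

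**Inputs from the Protocol**
- Baseline group: enrollees operated on before Covid (Aim 2).
- Comparison group: enrollees whose surgery Covid cancelled (Aim 2).
- Operated patients can have had an earlier cancellation: section 3.1.2 d) keeps patients who were postponed, or cancelled and later rescheduled, in their assigned group.
- Never-operated patients are expected: section 3.1.3, item 1.3, excludes randomized patients without surgery from all analyses, and item 5.2 allows 10% for no surgery and loss to follow-up combined.

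**Notation.** Among all pre-Covid enrollees scheduled for surgery, let c be the share never operated on and q the share cancelled, then rescheduled and operated on. The Protocol gives neither. The 10% allowance is a loose guide to how large c might be, because it also covers loss to follow-up.

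**Formulas**
- Ever cancelled, all scheduled enrollees: c + q.
- Ever cancelled, operated patients only: q / (1 − c).
- Failure to reschedule among cancelled, all scheduled enrollees: c / (c + q).
- Failure to reschedule among cancelled, operated patients only: 0 for any c, since everyone in the group was operated on.

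**Illustration (c and q assumed)**

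| c | q | Ever cancelled, all | Ever cancelled, operated only | Failure to reschedule, all | Failure to reschedule, operated only |
|---|---|---|---|---|---|
| 2% | 5% | 7.0% | 0.05/0.98 = 5.1% | 2/7 = 28.6% | 0% |
| 5% | 5% | 10.0% | 0.05/0.95 = 5.3% | 5/10 = 50% | 0% |
| 10% | 5% | 15.0% | 0.05/0.90 = 5.6% | 10/15 = 66.7% | 0% |

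The operated-only cancellation rate hardly moves (5.1% to 5.6%) while the rate in all scheduled enrollees more than doubles (7.0% to 15.0%). The shortfall is c(1 − c − q)/(1 − c). For c = q = 5% that is 0.05 × 0.90 / 0.95 = 4.7 percentage points, or nearly the whole of c.

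**The other side of the contrast.** In the Covid-cancelled group the cancellation rate is 100% by definition. Comparing it with any baseline rate says nothing about the pandemic.

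**GAD-2.** The instrument descriptions compare as follows.
- Section 3, item 1 (questionnaire content): PROMIS-10, Charlson, Oswestry, HOOS or KOOS.
- Section 3.1.2 a) (baseline): the same set.
- Section 3.1.2 f) (follow-up): HOOS or KOOS and PROMIS-10.
- Section 3.1.2.1 (schedule): the same instruments; PROMIS-10 and HOOS/KOOS at four time points.

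The GAD-2 is in none of them. It is named only in sub-study Aim 4.

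**The case against.** The best defence of Aim 2 is that its stated objective concerns one cohort, the patients Covid cancelled, followed to one year. Delay and failure to reschedule in that cohort can be estimated with no comparator. The text introducing the sub-study in section 1.2 also describes patients enrolled and scheduled before the national pause, a group not conditioned on surgery, so the Aim 2 wording may be loose shorthand for it. The first part stands. The second is plausible, but the aim itself names operated patients, and the main analysis drops never-operated patients, so an analyst following the text would leave them out.

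Four stronger readings are tempting and are not supported.

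- *The baseline cancellation rate is zero or cannot be estimated.* Section 3.1.2 d) lets operated patients have an earlier cancellation, so temporary cancellations and their delays can be counted. The rate is understated, not void. Only failure to reschedule is forced to zero.
- *A definite number of the roughly 300 patients would be wrongly attributed to Covid.* The Protocol nowhere subtracts a baseline failure rate or computes a Covid-attributable excess. Such a count would need both an assumed background rate and an attribution step that the Protocol does not contain.
- *Aim 4 cannot be answered.* The PROMIS-10 mental score and HOOS/KOOS are collected at baseline and at every follow-up, so it keeps a usable before/after contrast.
- *No pre-Covid GAD-2 values exist.* The expanded survey and the appendices are not shown, and section 1.2 describes the survey's recipients more broadly than Aim 1 does. What can be said is that no pre-Covid source is documented.

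**Conclusion.** The point holds for the definition of the Aim 2 baseline. As worded, it omits all permanent pre-Covid cancellations, understates the cancellation rate by close to the share never operated on, and makes pre-Covid failure to reschedule a structural zero. The contrast with a group that is entirely cancelled is not informative. The direction of the error follows from the definition alone. Its size depends on c and q, which the Protocol does not give: over the assumed range above, the understatement is 1.9 to 9.4 percentage points (7.0 − 5.1 and 15.0 − 5.6).

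The GAD-2 point holds as a secondary one: the instrument is named for a before/after comparison and is missing from every listed assessment.

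The Aim 2 rescheduling outcomes within the Covid-cancelled cohort, the rest of Aim 4, and the trial's primary and secondary analyses are unaffected. The correction is worth making because the defect lies in a stated definition and costs little to repair.

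**What to change.** **Aim 2.** Define the baseline cohort as all patients enrolled and scheduled for surgery in a comparable pre-pause window (for example the same calendar months), whether or not they were operated on. Compute the cancellation rate in all of them. Among those cancelled, compute rescheduling delay and failure to reschedule, and compare these with the Covid-cancelled patients on the same 12-month clock. State when that clock starts in each group. State also that the exclusion of never-operated patients in section 3.1.3, item 1.3, does not apply to this sub-study analysis.

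**Aim 4.** Rest the before/after distress comparison on the PROMIS-10 mental score. Report the GAD-2 descriptively among those who completed it, unless a pre-Covid source exists, in which case name it and add it to the instrument list.

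**Cost.** A few sentences of sub-study text. Patients are enrolled and randomized before surgery, so those never operated on can already be identified, and PROMIS-10 is already collected. The real work is looking up rescheduling dates for pre-Covid cancellations. The price under Aim 4 is losing the GAD-2 as a formal contrast if no earlier scores exist.

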## 2. BACKGROUND AND SIGNIFICANCE

### 2.1. Background

Osteoarthritis is the most common form of arthritis and involvement of the hip and knee is a leading cause of long-term disability and time missed from work. The societal burden of this condition is substantial. Elective total joint replacement of the hip (THA) and knee (TKA) comprise the most commonly performed procedures in the US, totaling nearly 1 million annually. Moreover, THA and TKA are increasing in number with the aging of the baby boomer generation and collectively stand out as the single largest expenditure for Medicare. Readmission to the hospital within 90 days of operation occurs after 10-15% of elective hip and knee replacements and venous thromboembolism (VTE; blood clots in the veins), specifically pulmonary embolism (PE; blood clots in the lung), is one of the most common causes. Despite advances in surgical and perioperative care, fatal PE occurs in 0.1 to 0.5% of patients and is responsible for more than 1,000 patient deaths each year following these operations. Appropriately, considerable effort has been directed at identifying the best method to prevent venous thromboembolism in these patients. However, use of potent anticoagulants soon after orthopaedic operations to reduce the risk of blood clots must be tempered by consideration of the bleeding risk implicit in these procedures. Orthopaedic surgeons typically opt for one of three main regimens for preventing these clots, and guideline recommendations for use of blood thinners have historically been conflicted. The ideal prophylaxis will represent a balance between the risk of fatal pulmonary embolism and the morbidity of bleeding resulting in a hematoma (old blood accumulating in the wound) or secondary infection related to anticoagulant use. Such a critical decision requires clear and definitive evidence about the potential benefits and harms of blood thinners used to prevent clots after operation, as well as knowledge of individual patient preferences about these tradeoffs and risks.

Not surprisingly, based on the remarkable success and popularity of total hip and knee replacement, its unique tendency to stimulate blood clot formation, and the substantial cost to Medicare for these operations, several Federal agencies and public entities have emphasized the importance of venous thromboembolism as a public health issue. The NIH last sponsored a Consensus Conference dedicated to this subject thirty years ago, in 1986. That panel concluded, “for high-risk orthopedic patients undergoing elective hip surgery or knee reconstruction ... low-dose warfarin, dextran, or adjusted dose-heparin” was “recommended... for at least 7 days” as prophylaxis. They noted these regimens reduced the rate of clinical PE, but “the lowered death rate from PE, while suggestive, is not statistically significant.” The panel also offered a note of caution; that “warfarin and dextran in commonly used doses can cause complications of operative bleeding and wound hematomas... (which) can be a significant problem in joint replacement patients.” Since then, some type of VTE prophylaxis has become “standard of care” after hip and knee replacement in the US. Yet, a singular “best practice” has remained elusive because of the complex balance between the benefits of PE prevention and the harms resulting from anticoagulant-related bleeding and its associated pain and disability.

There remain substantial gaps in evidence concerning the benefits and harms of anticoagulant use to prevent VTE after hip and knee replacement. In 2003, the NIH Consensus Conference on Total Knee Replacement concluded that, “the effectiveness of anticoagulation for the prevention of pulmonary emboli is unclear” and noted prophylaxis recommendations were based “primarily on the reduction of deep venous thrombosis detected by venography.” They went on, “the vast majority of DVTs following TKR are asymptomatic, and the available data indicate that prophylaxis does not alter the occurrence of symptomatic DVT or pulmonary embolism, although no individual study was large enough to statistically assess effects on the occurrence of PE.” They suggested that “a randomized, placebo-controlled trial of prophylactic anticoagulation that assesses the outcomes of PE, bleeding, wound complications, and death seems warranted.” In 2008 the Surgeon General issued a “Call to Action to Prevent Deep Vein Thrombosis and Pulmonary Embolism” based on its in-hospital and post-discharge morbidity and mortality, which was estimated to account for 100,000 to 180,000 deaths each year in the United States. The report called for research on the benefits and risks of preventive and therapeutic anticoagulation for the elderly and those undergoing total joint replacement. In June 2009, the Institute of Medicine included “anticoagulant therapies (eg low-intensity warfarin, aspirin, injectable anticoagulants) for patients undergoing hip or knee arthroplasty” among its national priorities for comparative effectiveness research. The paucity of adequately powered randomized trials providing credible data for clinically meaningful PE and bleeding events has left guideline workgroups unable to provide useful evidence-based recommendations for VTE prevention.

Historically, clinical guidelines from the American College of Chest Physicians (ACCP) and the American Academy of Orthopaedic Surgeons (AAOS) have long been at odds, resulting in confusion for both patient and physician over optimal management. The ACCP, a perennial authority on VTE prophylaxis, issued their first clinical practice

guidelines in 1992. Their guidelines historically relied exclusively on prospective randomized trials and favor potent anticoagulants with a primary endpoint of reducing DVT and PE and a relatively low concern for bleeding. Conversely, the AAOS has placed greater value on specific reduction of *clinical* VTE as a primary endpoint with a competing desire to mitigate surgical complications related to bleeding that may result in wound hematoma, re-hospitalization, re-operation, and removal of the joint prosthesis secondary to deep infection. In 2009, after specific recommendation *against* the use of aspirin by the ACCP, the AAOS first released clinical guidelines endorsing aspirin for patients at “typical” risk of VTE after hip and knee replacement and introduced an algorithm for risk stratification of patients. Aspirin was not recommended for patients perceived to be at “elevated” risk of VTE in favor of more potent anticoagulants and, for patients at “elevated” risk of bleeding, potent anticoagulants were omitted in favor of aspirin, warfarin, or mechanical compression devices alone. For patients with an “elevated” risk of *both* VTE and bleeding, less potent anticoagulant prophylaxis was recommended. The AAOS has consistently endorsed less intensive anticoagulation with aspirin or low intensity warfarin based on observational studies; both agents have been associated with comparable rates of clinical PE and less bleeding than more potent anticoagulants. From the surgeon’s perspective, increased bleeding is at least as worrisome as increased risk of PE; indeed, fatal PE occurs substantially less often than does untoward bleeding. Ultimately, reconciliation occurred with release of the 2nd AAOS and 9th ACCP clinical guidelines, with both groups conceding that *clinical* VTE and PE was the important endpoint and insufficient data existed to endorse any specific prophylaxis regimen as “best practice”. Perfect harmony was achieved in 2014 when the American College of Surgeons Surgical Care Improvement Project (SCIP) added aspirin to its list of acceptable VTE prophylaxis agents. All groups now decline to endorse a preferred regimen for VTE prophylaxis after THA and TKA, other than to recommend doing *something* to mitigate the risk of thrombosis following activation of the clotting cascade caused by these procedures.

At an international multidisciplinary workshop convened in 2011 by the PI ([name]) of this trial to gain stakeholder opinion on the subject of VTE prophylaxis after hip and knee replacement (Appendix A), the consensus among both surgeons and thrombosis experts was that clinical equipoise existed due to a paucity of data. Notwithstanding the large size of administrative datasets and national joint replacement registries, the observational nature of such data limits the meaningful information that they contribute to this discussion. Opinion leaders from both medical and surgical communities argued for conducting a large definitive clinical trial to better inform future treatment decisions. Shortly thereafter, in March 2012, the AHRQ released an exhaustive Comparative Effectiveness Review on VTE prophylaxis in orthopaedic surgery and suggested “there are inadequate data to say whether or not deep vein thrombosis causes pulmonary embolism or is an independent predictor of pulmonary embolism. The balance of benefits to harms is favorable for providing prophylaxis ... and to extend the period of prophylaxis beyond the standard 7-10 days.” While the report offered that low molecular weight heparins were superior to unfractionated heparin, an agent abandoned for orthopaedic VTE prophylaxis decades ago, it concluded that “other interclass comparisons either could not be made due to lack of data, showed similarities between classes on outcomes, or had offsetting effects where benefits of one class on efficacy was tempered by an increased risk of bleeding.” They recommended that comparative clinical trials should focus directly on final health outcomes rather than DVT as a surrogate and “include more outcomes assessing harms such as bleeding leading to infection, bleeding leading to transfusion, readmission and reoperation to provide more information for the comparative balance of benefits to harms.” In keeping with the convergence of ACCP and AAOS guidelines, the Joint Commission, Center for Medicare and Medicaid Services, and the Surgical Care Improvement Project (SCIP) all now mandate VTE prophylaxis after THA and TKA but none endorse any regimen as “best practice”.

Central to this impasse is the acknowledged absence of both clinical VTE and health outcomes endpoint data along with an increased appreciation of the morbidity associated with adverse bleeding events, particularly as perceived by the patient and highlighted by the recent ACCP guidelines. Each of these events occurs so infrequently that nearly 25,000 patients would be needed to derive statistically valid conclusions from a single clinical trial, and no existing studies satisfy this requirement of scale. As a result, specific recommendations to guide patients and physicians in making critical decisions regarding perioperative VTE prophylaxis after hip and knee replacement remain elusive. The ideal prophylaxis represents a balance between the risk of VTE, including death from PE, and the morbidity of bleeding complications associated with anticoagulation used to prevent VTE (table). Most physicians focus on prevention of fatal PE, orthopaedic surgeons desire at least equally to avoid untoward bleeding, and patients invoke less well-represented concerns about quality of life and eventual function indirectly related to both issues. The specific preferences and risk tolerances of individual patients greatly influence the choice of anticoagulant that carries a risk of bleeding and the potential to compromise function. It is logical, therefore, that one patient might elect a less potent anticoagulant such as aspirin, which has a slightly greater risk of death from PE but with the benefit of a greatly reduced likelihood of bleeding,

while another might choose a potent anticoagulant that maximally reduces the risk of death from PE despite a higher risk of related bleeding. There are few more compelling scenarios demanding genuine consideration of outcomes important to patients than an elective operation with a track record of dramatically improving quality of life that also carries a small, but real, risk of death and a greater risk of associated complications that compromise function. A recent report on the risk-benefit tradeoffs that must be considered in electing to undergo TKA vividly illustrates the complex decision analysis faced by more than one million patients each year in the US who undergo total joint replacement.31a

